5.1.5 Criteria for Second Induction Cycle

A bone marrow aspirate and biopsy is performed on day 12-14 (\pm 1 day), i.e. 5-7 days after the completion of the cytarabine infusion or 7-9 days after completion of clofarabine treatment. The decision to administer a second induction cycle is based on the following criteria:

NOTE: Patients undergoing 2nd induction who do not achieve complete response by day 56 of the start of re-induction will be taken off protocol treatment.

Rev. 2/12,
2/13

5.1.5.1 If the marrow cellularity is judged to be greater than 20%, or not markedly/moderately hypocellular on the marrow biopsy, or with > 5% blasts, or the bone marrow is indeterminate, then repeat induction is indicated.

If the marrow cellularity is less than markedly hypocellular, or moderately hypocellular, or there are persistent circulating blasts, then the patient's status should be followed with a repeat marrow assessment within 5 to 7 days.

5.1.5.2 Second Induction Treatment Dose Arm A & Arm B

For Arm A, the 2nd induction cycle is a repeat of the initial induction and at the same schedule of chemotherapy as the 1st induction, however, for Arm B, clofarabine is administered at the reduced dose of **20** mg/m²/day IV by 1 hour infusion days 1-5, and should not start before day 21. Prior to administering a 2nd cycle of clofarabine induction, abnormalities in hepatic function must have returned \leq grade I.

5.1.6 Consolidation

Rev. 2/13

All patients achieving CR or CRi will receive consolidation therapy when fit. Patients with an HLA-matched donor who achieve at least a 'morphologic leukemia-free state' ⁷⁹ (< 5% blasts without hematologic recovery, and negative flow cytometry if performed) will be eligible for AlloSCT (see Section [5.1.7](#)). Patients will be assigned to consolidation based upon the 1st randomization: those randomized to 'standard' daunorubicin & cytarabine induction will receive 2 cycles at 4-6 week intervals of 'standard' intermediate-dose Cytarabine 1500 mg/m² q 12 hours for either 12 doses per cycle (age 60-69 years) or 6 doses per cycle (age \geq 70 years); those randomized to 'clofarabine' will receive 2 cycles of clofarabine 20 mg/m²/day x 5 days at 4-6 week intervals.

Arm C 'Intermediate-Dose Cytarabine' Consolidation

- All patients randomized to 'standard' daunorubicin & cytarabine induction

- 2 cycles of consolidation therapy
- Cytarabine 1500 mg/m² IV over 1 hour stratified by age for either twice a day (q 12 hours) 12 doses per cycle (age 60-69 years) or once daily days 1-6, 6 doses per cycle (age \geq 70 years).

Cycles will be repeated at 4-6 week intervals.

Arm D 'Clofarabine' Consolidation

- All patients randomized to clofarabine induction
- 2 cycles of consolidation therapy
- Clofarabine 20 mg/m²/day infused over 1 hour x 5 days per cycle

Cycles will be repeated at 4-6 week intervals.

NOTE: Consolidation for Patients Proceeding to Transplant

- Up to 1 cycle of consolidation treatment is allowed
- Treatment determined by induction

5.1.6.1 Consolidation Cycle 1

Patients who achieve a CR or CRI and have no residual significant toxicities from the induction course are eligible for further protocol therapy. In general, consolidation therapy should start within 1 month of documentation of CR/CRI when possible, after the resolution of any non-hematologic toxicity of previous chemotherapy (to </= grade I), and with recovery of performance status to >/= baseline in the judgment of the Investigator. The first cycle of post-remission therapy must begin within sixty days of documentation of a CR or CRI. A repeat measurement of ejection fraction should be performed for patients on Arm C and Arm D. Patients on Arm C will receive dose-escalated cytarabine.

The schedule of cytarabine administration is modified based upon age < or \geq 70 years.

5.1.6.2 Consolidation Cycle 2

Patients must have maintained peripheral blood evidence of a remission as defined in Section [6.1](#). Consolidation cycle 2 should commence within thirty days of recovery of peripheral blood counts after consolidation cycle 1.

Patients who do not begin consolidation cycle 2 within 60 days of recovery are ineligible for further protocol therapy.

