5.4.1 Dose Modification for Cytarabine – Arm C Consolidation

For patients \geq 70 years of age the cytarabine dose is identical but the patient will receive one dose daily for a total of 6 doses (days 1-6).

Patients should have a daily creatinine and total bilirubin. The dose of cytarabine will be adjusted. The dose of cytarabine will be adjusted if there is a change in the serum creatinine or bilirubin during that cycle after the start of therapy.

Serum Creatinine (mg/dL)	Serum Total Bilirubin	Dose (mg/m ²)
< 2	< 3	1500
> 2 (or an increase of > 0.5 mg/dL from baseline)	< 3	750
> 3	< 3	500
Any	> 3	500

Modified from Smith, et al. JCO 15:833

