5.5 Supportive Care

All supportive measures consistent with optimal patient care will be given throughout the study.

5.5.1 Cytarabine Consolidation- Arm C- Cycles 1 and 2

Patients must receive corticosteroid eye drops, 2 drops in each eye at least 4 times a day starting on day 1 before the first dose of cytarabine and continuing until at least 48 hours after completion of cytarabine, i.e. for a minimum of 8 days.

Cytarabine Age 60-69 1500 mg/m² as a one hour intravenous infusion every 12 hours for a total of 12 doses (days 1-6) times 2 cycles.

		Age \geq 70 1500 mg/m ² as a one hour intravenous infusion every 24 hours for a total of 6 doses (days 1-6) times 2 cycles.
	Corticosteroid	2 drops in each eye, 4 times a day for 10 days. The eye drops should be applied within one hour of the administration of high dose cytarabine.
	GM-CSF	250 mcg/m ² /day by intravenous or subcutaneous injection starting one day after the last dose of cytarabine through recovery of absolute neutrophil count (ANC) \geq 500 cells/mcL is sustained for 3 consecutive days. The dose may be rounded to the nearest vial size.
	OR G-CSF	5 mcg/kg/day by either intravenous or subcutaneous injection starting one day after the last dose of cytarabine, through recovery of absolute neutrophil count (ANC) \geq 500 cells/mcL is sustained for 3 consecutive days. The dose may be rounded to the nearest vial size.
	OR Pegfilgrastim	6mg SC on day 7 (1 day after completing the last dose of cytarabine).
Rev. 2/12	5.5.2	
Supportive Care with GM-CSF, G-CSF & Prophylactic Antibiotics for Restaging Bone Marrow
 
Patients who achieve an aplastic BM following the 1st or 2nd course of induction therapy should receive cytokine support with GM-CSF (LeukineTM) at a dose of 250 mcg/m²/day subcutaneously every day until calculated ANC \geq 5000/mcL or discharge from hospital. Alternatively, patients may receive G-CSF at a dose of 5 mcg/kg (rounded to the nearest vial size) at the discretion of the treating physician.
 
Patients should receive an oral Quinolone, Fluconazole, and Acyclovir to prevent infection once the ANC drops below 1000 beginning sooner than day 7 of induction.

Rev. 2/12	5.5.3	Arm D Clofarabine Consolidation

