8.1.5 Dose Specifics

Induction Arm A

100 mg/m²/day by 24 hour continuous infusion for 7 days (days 1-7).

Consolidation I

1500 mg/m² as a one hour intravenous infusion every 12 hours for a total of 12 doses (days 1-6) for patients < 70 years of age, or a total of 6 doses for patients ≥ 70 years of age. See Section [5.4.1](#) for dose modifications for Consolidation I. See Section [5.6.3](#) for duration of Consolidation II therapy.

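### The opening paragraph of section 5.1.6 gives cytarabine every 12 hours to patients aged 70 and over, where the rest of the protocol gives it once daily

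*Combined protocol and SAP*

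**What the plan says.** The schedule of Arm C consolidation cytarabine (1500 mg/m² per dose, two cycles) is stated or touched on in six places.

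- **5.1.6, opening paragraph:** "q 12 hours for either 12 doses per cycle (age 60-69 years) or 6 doses per cycle", the second option being for age 70 and over.
- **5.1.6, Arm C bullet:** twice a day for age 60-69, "or once daily days 1-6, 6 doses per cycle" for age 70 and over.
- **5.1.6.1:** "The schedule of cytarabine administration is modified based upon age", with the cut at 70.
- **5.4.1:** at 70 and over, "the patient will receive one dose daily for a total of 6 doses (days 1-6").
- **5.5.1:** age 60-69, "every 12 hours for a total of 12 doses (days 1-6) times 2 cycles"; age 70 and over, "every 24 hours for a total of 6 doses (days 1-6) times 2 cycles".
- **8.1.5:** "every 12 hours for a total of 12 doses (days 1-6) for patients < 70 years of age, or a total of 6 doses" for age 70 and over, with a pointer to 5.4.1 for dose modifications.

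Section 5.5.1 also ties supportive care to the end of the course. Pegfilgrastim, one of three growth-factor options, is given as "6mg SC on day 7 (1 day after completing the last dose of cytarabine"). Corticosteroid eye drops must continue for at least 48 hours after cytarabine ends, which the section equates to a minimum of 8 days.

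**The concern.** In the opening paragraph the 12-hour interval is stated before the two alternatives, so grammatically it applies to both. Age then changes only the number of doses, and the older group gets a short course at the younger group's daily dose. Everywhere else that an interval is given for the older group, it is 24 hours.

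This is a current chemotherapy instruction in the treatment plan. A site working from it would remove the daily-dose reduction for the oldest patients. Section 5.4.1 asks for daily creatinine and bilirubin so that cytarabine can be adjusted within the cycle; at 12-hour intervals two doses, not one, would be given for each daily result. The day-7 pegfilgrastim would also fall several days later than its own definition allows.

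**Working it through.** No figure in the statistical section depends on this point, so the check is a comparison of texts with dose arithmetic. Inputs: 1500 mg/m² per dose; 6 doses per cycle at age 70 and over; 12 doses per cycle at age 60-69; interval 12 or 24 hours.

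**Cycle total = doses × dose level**

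- Age 70 and over: 6 × 1500 = 9000 mg/m², on either interval.
- Age 60-69: 12 × 1500 = 18000 mg/m².

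**Daily dose = (24 ÷ interval in hours) × dose level**

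- Age 70 and over, 12-hourly: 2 × 1500 = 3000 mg/m² per 24 hours.
- Age 70 and over, once daily: 1 × 1500 = 1500 mg/m² per 24 hours.
- Age 60-69, 12-hourly: 2 × 1500 = 3000 mg/m² per 24 hours.

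**Timing of the last dose, age 70 and over**

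- Once daily: hours 0, 24, 48, 72, 96, 120, so the last dose is on day 6.
- 12-hourly: hours 0, 12, 24, 36, 48, 60, so the last dose is on day 3 with a morning start and day 4 with an evening start.

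| Age 70 and over | Opening paragraph of 5.1.6 | Arm C bullet, 5.4.1, 5.5.1 |
|---|---|---|
| Interval | 12 h | 24 h |
| Cycle total | 9000 mg/m² | 9000 mg/m² |
| Daily dose | 3000 mg/m² | 1500 mg/m² |
| Daily dose relative to age 60-69 | 3000/3000 = 1.0 | 1500/3000 = 0.5 |
| Cycle total relative to age 60-69 | 9000/18000 = 0.5 | 9000/18000 = 0.5 |
| Last dose | day 3 (or 4) | day 6 |
| Day-7 pegfilgrastim after last dose | 4 (or 3) days | 1 day |

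**Which reading is intended.** Three statements give one dose a day over days 1-6. Two supportive-care instructions in 5.5.1 fit only a six-day course: day 7 is one day after the last dose only if that dose is on day 6, and the eye-drop minimum is 6 days + 2 days = 8 days. A three-day course would give 3 + 2 = 5 days.

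**Section 8.1.5.** It attaches the 12-hour interval and days 1-6 to patients under 70 and states no interval of its own for the older group. It can be misread in the same way, but it points to 5.4.1, where the once-daily schedule is given.

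**The case against.** The strongest reply is that the opening paragraph only summarises how patients are allocated to consolidation. The working order is the Arm C block directly beneath it, which is complete and correct, and 5.4.1 and 5.5.1 repeat it. Dose level, dose count and cycle total agree wherever they are stated; only one interval in one sentence is off. This limits the risk. It does not remove the conflict, because the sentence is itself worded as an order and nothing says which text prevails.

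Some narrower points are fair:

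- Section 5.1.6.1 is weak evidence. A schedule modified by age could also describe 12 versus 6 doses at one interval. The conclusion does not need it.
- Only the pegfilgrastim option names day 7. GM-CSF and G-CSF start one day after the last cytarabine dose and would follow either schedule.
- Section 8.1.5 is worded much like the opening paragraph, so it is reasonable to clarify both together.
- Reach is narrow. Step 1 accrual was suspended on February 23, 2015. Under section 9.5 further patients enter only if the conditional power for the maintenance comparison exceeds 0.7. They would then receive consolidation on study, although 9.5 does not spell out the regimen.

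**Conclusion.** The concern holds. The opening paragraph of 5.1.6 is wrong as written for age 70 and over: it gives 3000 mg/m² a day over about 3 days where the protocol elsewhere gives 1500 mg/m² a day over 6 days. The cycle total of 9000 mg/m² is unchanged. The day-3 finish assumes a morning start.

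It should be fixed, but the exposure is small. No misdosing is documented. If the study reopens, about 74 patients in CR or CRi would be pre-registered; the documents do not say how many would be 70 or over and receive cytarabine. The endpoint definitions, significance levels, power, event counts and analyses are unaffected.

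**What to change.** Reword the cytarabine clause in the opening paragraph of 5.1.6 to read: cytarabine 1500 mg/m² every 12 hours × 12 doses (days 1-6) for age 60-69; 1500 mg/m² once daily (every 24 hours) × 6 doses (days 1-6) for age 70 and over. For clarity, add the once-daily interval for age 70 and over to 8.1.5. Leave the Arm C bullet, 5.1.6.1, 5.4.1 and 5.5.1 as they are on this point.

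The cost is a few words in one sentence plus the optional addition, with no change to any analysis. It should be in place before any reopening.

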3.2.7 Consolidation Criteria, Step 2 for Arms C and D

NOTE: All patients achieving CR or CRI will receive consolidation when fit.

NOTE: Patients proceeding to transplant are allowed up to one cycle of consolidation treatment.

3.2.7.1 Consolidation Cycle 1 must commence within sixty days of the bone marrow aspirate and biopsy that confirmed the presence of a CR or CRI.

3.2.7.2 Patients must have achieved a CR or Cri (or morphologic leukemia-free state for those patients proceeding to Arm G transplant) as defined in Section [6](#).

3.2.7.3 Patients who have achieved a CR or CRI must have maintained peripheral blood evidence of a CR or CRI as defined in Section [6](#).

Rev. 2/13

3.2.7.4 Patients must have an ECOG performance status of 0-2.

3.2.7.5 Patients must have resolved any serious infectious complications related to induction.

NOTE: Patients with an HLA-matched donor and proceeding to transplant will be allowed up to one cycle of consolidation treatment.

3.2.7.6 Any significant medical complications related to induction must have resolved.

3.2.7.7 Patients must have a creatinine and AST \leq grade 1 (refer to Section [5.4](#) for dose modifications). The values must be obtained within 48 hours prior to registration.

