3.2.8 Maintenance Criteria, Step 3 for Arms E and F

3.2.8.1 Maintenance should commence within 60 days of recovery of peripheral blood counts after Consolidation Cycle 2. Patients must begin Consolidation Cycle 2 within 60 days of recovery to be eligible for further therapy.

3.2.8.2 Patients must have maintained peripheral blood evidence of a remission as defined in Section [6](#) and must have a CR or CRi, confirmed on restaging BM aspirate and biopsy and cytogenetic analysis.

3.2.8.3 Patients must have an ECOG performance status of 0 -2.

3.2.8.4 Patients must have resolved any serious infectious complications related to Consolidation Cycle 2.

3.2.8.5 Any significant medical complications related to Consolidation Cycle 2 must have resolved.

3.2.8.6 Patients must have a total serum bilirubin \leq 1.5 x ULN and a serum creatinine \leq grade 1. The values must be obtained within 48 hours prior to randomization.

NOTE: If total bilirubin is 2-3 mg/dL, but direct bilirubin is normal, then the patient will be considered eligible.

3.2.8.7 The ANC must be $>$ 1000 mm³ and the platelet count $>$ 75,000 mm³ prior to starting every cycle of treatment with decitabine. Decitabine may be delayed for up to 4 weeks between cycles (i.e. may be administered as infrequently as q8 weeks) while waiting for counts to recover.

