6.1 Complete Remission (CR)

Requires that all of the following be present:

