6.1.1 Peripheral Blood Counts

6.1.1.1 Neutrophil count $\geq 1.0 \times 10^9 / L$.

6.1.1.2 Platelet count $\geq 100 \times 10^9 / L$.

6.1.1.3 Reduced hemoglobin concentration or hematocrit has no bearing on remission status.

6.1.1.4 Leukemic blasts must not be present in the peripheral blood.

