6.2 Complete Remission incomplete (CRI)

All the same response criteria in peripheral blood and bone marrow as CR with the exception that there is incomplete platelet recovery (platelets $> 50 \times 10^9 / L$ independent of platelet transfusions) over a period of observation without evidence of ongoing platelet recovery and no sooner than day 35 after the preceding cycle of treatment.

Rev. 8/13

6.2.1 Patients who achieve criteria for CR or CRI and who have recovered from the effects of therapy but who have **< 20% cellularity in BM** will be deemed a "Hypocellular CR/CRI" and will be allowed to continue protocol therapy at the discretion of the Investigator and after discussion with the Study Chair as long as they meet other eligibility criteria for Step 2

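### Section 5.1.6.2 ties consolidation cycle 2 to the CR definition alone, which shuts out persistent CRi patients whom Section 5.1.6 and the neighbouring criteria include

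*Combined protocol and SAP*

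**What the plan says.** Section 5.1.6.2 (Consolidation Cycle 2) opens with a mandatory condition: "Patients must have maintained peripheral blood evidence of a remission as defined in Section [6.1". The section cited is headed "6.1 Complete Remission (CR") and, at 6.1.1.2, requires platelets of at least 100 x10^9/L. CRi has its own Section 6.2: the CR criteria are met except that platelets, above 50 x10^9/L without transfusion, have not fully recovered. That state has to be seen "over a period of observation without evidence of ongoing platelet recovery and no sooner than day 35 after the preceding cycle of treatment".

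Section 5.1.6, the parent section, states: "All patients achieving CR or CRi will receive consolidation therapy when fit". It specifies two cycles in Arm C and two in Arm D, with at most one for patients proceeding to transplant.

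Two other criteria use nearly the same formula. For Step 2, 3.2.7.3 says responders "must have maintained peripheral blood evidence of a CR or CRI as defined in Section" 6. For Step 3, 3.2.8.2 says: "Patients must have maintained peripheral blood evidence of a remission as defined in Section [6](#) and must have a CR or CRi".

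Sections 5.1.6.2 and 3.2.8.1 both make a patient ineligible for further protocol therapy if cycle 2 has not begun within 60 days of recovery. Under 5.1.8.2, patients who do not qualify for the maintenance randomisation are followed as in Arm E.

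**The concern.** The condition for cycle 2 is an operative treatment rule, and it points to a definition that a CRi patient cannot meet. Platelet recovery is what separates CRi from CR, and it is a peripheral blood criterion, which is exactly what 5.1.6.2 asks the site to check. A site following 5.1.6.2 withholds cycle 2 from a patient in persistent CRi; a site following 5.1.6 gives it.

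The difference can carry forward. Starting cycle 2 is a condition for Step 3, so the first patient may never be randomised to decitabine or observation while the second may be.

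**Working it through.** The plan has no figure to reproduce here. The check sets the texts side by side and then asks whether the situation can arise on schedule.

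**Response required at each step**

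| Point in treatment | Section | Definition cited | CRi accepted? |
|---|---|---|---|
| Before cycle 1 (Step 2) | 3.2.7.3 | Section 6 | Yes, named |
| Consolidation overall, two cycles | 5.1.6 | CR or CRi | Yes, named |
| Before cycle 2 | 5.1.6.2 | Section 6.1 | No, if read literally |
| Before maintenance (Step 3) | 3.2.8.2 | Section 6 | Yes, named |

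Only 5.1.6.2 cites 6.1. The sentence in 3.2.8.2 opens with the same words but cites Section 6 and adds CRi. That makes a cross-reference left too narrow the likely explanation.

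**Who falls in the gap** (platelets, x10^9/L)

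- 6.1.1.2: at least 100.
- 6.2: above 50, transfusion-independent, no ongoing recovery, not before day 35.
- Gap from citing 6.1 alone: persistent CRi with platelets above 50 and below 100. Patients whose counts are still rising are not in the gap; they wait.

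**Other thresholds**

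- 3.2.8.7 and 5.1.8.1 require platelets above 75 before each decitabine cycle. A stable CRi patient at 80 meets that limit (80 > 75) but fails the cycle 2 condition leading to it (80 < 100).
- 5.4.4.1 accepts platelets of 50 or more for clofarabine consolidation in patients who had achieved CRi. It is worded for the cycle after induction, so it shows intent and does not settle cycle 2.

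**Can this arise within the planned schedule?**

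- Section 5.1.6: "Cycles will be repeated at 4-6 week intervals". 4 x 7 = 28 and 6 x 7 = 42, so cycle 2 is due on days 28 to 42.
- If day 35 in 6.2 is counted from day 1 of the preceding cycle, CRi can be called on days 35 to 42 of that window.
- If it is counted from the last dosing day (an assumption), CRi can be called from day 35 + 5 = 40 on Arm D (5 dosing days) or 35 + 6 = 41 on Arm C (6 dosing days). Both are at or before day 42.

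**What happens next to the patient**

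- If stable CRi counts count as recovery, the 60-day limit in 5.1.6.2 and 3.2.8.1 starts and runs out without cycle 2. The patient becomes ineligible for Step 3.
- If only 6.1 counts are recovery, the limit never starts and cycle 2 stays on hold with no stated end.

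Sections 5.1.8.1, 9.1 and 9.5 do not directly contradict 5.1.6.2. They describe CR or CRi patients moving towards the second randomisation, which supports the view that CRi patients were meant to stay on that path.

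**The case against.** The strongest reply is that 5.1.6.2 is a specific continuation rule qualifying a general plan, and could be deliberately stricter. The other criteria apply at different times: 3.2.7.3 before cycle 1, and 3.2.8.2 after consolidation is complete. A patient could have CR counts before cycle 2 and CRi after it, since cycle 2 is itself myelosuppressive. So accepting CRi at Step 3 does not by logic exclude a CR requirement before cycle 2. Footnote 9 to the Section 7.1 calendar also refers to CR-range counts before Consolidation II, and Section 1.1.2 reports that toxicity in consolidation limited most patients in an earlier clofarabine trial to two courses.

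Part of this stands. The documents do not state the intent, so a deliberate rule cannot be strictly ruled out. But footnote 9 only waives a repeat marrow and does not decide who receives cycle 2. No rationale is given for accepting CRi before cycle 1, refusing it before cycle 2 and accepting it again before maintenance. Such a rule also sits badly with the decitabine platelet limit of 75.

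A softer reading treats the sentence as a check that the patient has not relapsed, with doubtful cases going to the study chair. That may be how sites would use it, but it departs from the section cited.

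It is also fair to say that loss of the randomisation is conditional, and that 5.1.6.2 times cycle 2 from count recovery. The day 35 to 42 overlap shows only that the situation can occur on schedule.

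**Conclusion.** The inconsistency is real and should be corrected. Taken literally, 5.1.6.2 denies cycle 2 to patients in persistent CRi who are not going to transplant, against 5.1.6 and out of line with 3.2.7.3 and 3.2.8.2, and it can cost them the maintenance randomisation.

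The size is limited. The number of patients affected cannot be derived, because the documents give no CRi share after cycle 1. No sample size, power or event figure is wrong. The rule acts before the second randomisation, so it does not bias Arm E against Arm F.

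Step 1 accrual was suspended in February 2015, with 120 patients already in the second randomisation. Under 9.5 the study reopens only if conditional power exceeds 0.7. It would then pre-register about 74 CR/CRi patients, give them consolidation on study, and aim for 52 more randomisations (120 + 52 = 172). Those patients would be under this rule.

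**What to change.** In 5.1.6.2, replace the reference to Section 6.1 with a CR or CRi as defined in Section 6 (6.1 or 6.2), for both Arm C and Arm D. Leave the marrow-waiver wording in footnote 9 of Section 7.1 as it is. The change should be made before any reopening under 9.5. It costs one cross-reference, with no new procedures, visits or patients.
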